Moreover, analyses of nonclinical studies in Sprague Dawley (SD) rats have shown that oral administration of hAd5-S-Fusion+N-ETSD results in no remarkable changes in clinical signs, hematology, clinical pathology, or urinalysis. Similarly, studies in non-human primates (NHPs) have shown that SC injection of hAd5-S-Fusion+N-ETSD followed by oral administration of enteric-coated capsules in rhesus macaques did not result in any treatment-related toxicities post a single SC injection or 7 days after an oral boost. Preliminary analysis of results from these studies have shown that all vaccinated NHP generated anti-S IgG and following SARS-CoV-2 challenge, viral replication was inhibited in all vaccinated NHP from day 1 post-challenge with complete protection in both nasal passages and lung. Furthermore, replicating SARS-CoV-2 dropped immediately and was undetectable as soon 3 days post-challenge in some NHP. In contrast, placebo-controlled animals demonstrated ongoing viral replication.

Together, these data suggest that the hAd5-S-Fusion+N-ETSD (Suspension for injection) is well tolerated when administered to human subjects SC; that there is little evidence of toxicity associated with the oral formulation of hAd5-S-Fusion+N-ETSD in either rodents or NHP; and further, that the combination holds promise in stimulating SARS-CoV-2-specific antibody production and rapid viral clearance. Advantages of the oral vaccine formulation are 1) that it offers ease of administration and the potential to increase patient compliance with scheduled vaccinations and 2) that it incorporates the gastrointestinal tract into the antigen sampling mechanism and therefore, the resultant immunity, which may result in the production of mucosal immunity and protection from invasion of epithelial tissues by SARS-CoV-2 virus. Intramuscular (IM) administration of hAd5-based COVID-19 vaccines has not been explored in clinical trials, but hAd5 [E1-] vectors have been administered IM in human clinical trials and currently authorized vaccines have utilized this route of administration with proven effectiveness. Moreover, one vaccine authorized by FDA, Janssen Ad26.COV2.S, employs an adenovirus vector and is administered IM. Therefore, we have included IM administration of hAd5-S-

Fusion+N-ETSD in the current study to allow the comparison of safety and immunogenicity to SC administration.

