This is a phase 1b, open-label study in adult healthy subjects. This clinical trial is designed to assess the safety, reactogenicity, and immunogenicity the combination of hAd5-S-Fusion+N-ETSD (Suspension for injection) and hAd5-S-Fusion+N-ETSD (Oral capsule) and to select an optimal combination dose for future studies.

The study will be divided into 2 stages. Up to 50 healthy subjects will be enrolled to evaluate the safety, reactogenicity, and immunogenicity of 5 different treatment regimens. In this evaluation stage, subjects will be divided into 5 dosing cohorts with dosing schedule, mode of administration, and dosage as follows:

Cohort	Number of Subjects	Dosing Schedule	Mode of Administration	Dosage
1	10	Day 1	SC	1×10^{11} VP/dose (4×10^9 infectious units [IU]/dose)
			Oral (PO)	1×10^{10} IU/dose
		Day 22	SC	1×10^{11} VP/dose (4×10^9 IU/dose)
2	10	Day 1	SC	1×10^{11} VP/dose (4×10^9 IU/dose)
			PO	1×10^{10} IU/dose
		Day 22	PO	1×10^{10} IU/dose
3	10	Day 1	PO	1×10^{10} IU/dose
		Day 22	PO	1×10^{10} IU/dose
4	10	Day 1	SC	1×10^{11} VP/dose (4×10^9 IU/dose)
			PO	1×10^{10} IU/dose
		Day 15	PO	1×10^{10} IU/dose
		Day 22	PO	1×10^{10} IU/dose
5	10	Day 1	Intramuscular (IM)	1×10^{11} VP/dose (4×10^9 IU/dose)
			PO	1×10^{10} IU/dose
		Day 22	PO	1×10^{10} IU/dose

PO (oral) doses are ± 0.5 log.

Number of IU in this table and throughout protocol was calculated in accordance with Certificate of Analysis (COA) for lot number CO5028002.

For subjects in cohorts 1 and 2, hAd5-S-Fusion+N-ETSD (Suspension for injection) and hAd5-S-Fusion+N-ETSD (Oral capsule) will be administered on day 1 (prime). Subjects in cohort 1 will be administered hAd5-S-Fusion+N-ETSD (Suspension for injection) again on day 22 (boost) and subjects in cohort 2 will be administered hAd5-S-Fusion+N-ETSD (Oral capsule) on day 22 (boost). For subjects in cohort 3, hAd5-S-Fusion+N-ETSD (Oral capsule) will be administered on days 1 (prime) and on day 22 (boost). For subjects in cohort 4, hAd5-S-Fusion+N-ETSD (Suspension for injection) and hAd5-S-Fusion+N-ETSD (Oral capsule) will be administered on day 1 (prime) and hAd5-S-Fusion+N-ETSD (Oral capsule) will be administered on days 15 (boost) and 22 (boost). For subjects in cohort 5, hAd5-S-Fusion+N-ETSD (Suspension for injection) and hAd5-S-Fusion+N-ETSD (Oral

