capsule) will be administered on day 1 (prime) and hAd5-S-Fusion+N-ETSD (Oral capsule) will be administered on day 22 (boost). Subjects in cohorts 1, 2, and 4 will be administered hAd5-S-Fusion+N-ETSD (Suspension for injection) via SC injection and subjects in cohort 5 will be administered hAd5-S-Fusion+N-ETSD (Suspension for injection) via IM injection.

Enrollment of the first 6 subjects will be staggered, with no more than 3 subjects enrolled per day for the first 2 days. On each of these days, vaccinations will occur at \geq 3 hour intervals. Safety for these 6 subjects will be assessed by telephone follow up 24 and 48 hours after receiving the priming vaccination. The ImmunityBio Safety Review Committee (SRC) will conduct a review of 48 hour safety data on the first 6 subjects; vaccination of additional subjects will proceed if no safety concerns are identified.

Up to 25 additional subjects will be enrolled in the expansion stage of the study. Based on safety and immunogenicity data gathered from cohorts 1–5, one treatment regimen will be selected for administration to subjects in cohort 6.

In addition to dosing visits described above, all subjects will have follow up study visits for the collection of safety, reactogenicity, and/or immunogenicity data. Additional follow up for safety information will occur via telephone contact as noted in the Schedule of Events.

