Safety will be assessed for all subjects and will include monitoring of vital signs, and incidence and severity of AEs. Blood samples will be collected for hematology and chemistry analyses and urine samples will be collected for urinalysis. Toxicities will be graded using the Guidance for Industry: Toxicity Grading Scale for Healthy Adult and Adolescent Volunteers Enrolled in Preventive Vaccine Clinical Trials (2007). Solicited local and systemic AEs will be collected using diaries for 7 days following any dose of vaccine. Solicited local AEs to be assessed following both SC and IM administration include pain, itching, induration, swelling, and erythema at the injection site. Bleeding, bruising, and tingling/numbness will also be assessed following IM administration. Solicited systemic AEs to be assessed include chills, fever, nausea, vomiting, diarrhea, headache, fatigue, myalgia, and abdominal pain/discomfort. Unsolicited AEs will be recorded in a diary from time of first vaccine dose until 30 days after last vaccine dose. Safety visits and telephone calls will occur at scheduled times for one year after the last vaccine dose, and will be used to collect unsolicited AEs for 30 days post last vaccine dose, all MAAEs and SAEs for 6 months post last vaccine dose (related MAAEs and SAEs at any time), as well as any solicited AEs continuing beyond the 7-day period after vaccination.

Immunogenicity analyses will be conducted by collecting serum and peripheral blood mononuclear cell (PBMC) samples from individual patients before and after vaccinations to test for humoral- and cell-mediated immune responses. Neutralizing antibodies will be assessed. Immunogenicity assessments will be conducted for 1 year after the last vaccine dose.

Enrollment (planned):

Up to 75 subjects will be enrolled in this study.

Eligibility Criteria:

Inclusion Criteria:

1. Healthy adults, age 18 – 55 years, inclusive, at time of enrollment.
2. Able to understand and provide a signed informed consent that fulfills the relevant Institutional Review Board (IRB) or Independent Ethics Committee (IEC) guidelines.
3. Agrees to the collection of biospecimens (eg, nasopharyngeal [NP] swabs and saliva) and venous blood per protocol.

4. Ability to attend required study visits and return for adequate follow-up, as required by this protocol.
5. Ability to swallow a capsule.
6. Temperature < 38°C.
7. Negative for SARS-CoV-2 (qPCR or LAMP test).

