Number of IU in this figure and throughout the protocol is calculated in accordance with Certificate of Analysis (COA) lot number CO5028002.

Abbreviations: hAd5 IM, hAd5-S-Fusion+N-ETSD (Suspension for injection) administered intramuscularly; hAd5 SC, hAd5-S-Fusion+N-ETSD (Suspension for injection) administered subcutaneously; hAd5 PO, hAd5-S-Fusion+N-ETSD (Oral capsule) administered by mouth (oral); IU, infectious units; VP, viral particles.

Table 10: Evaluation Stage (Cohorts 1–5): Schedule of Events

Study Period	Baseline/ Screening ^a	Vaccine Administration and Initial Follow Up							Extended Follow Up						EOS	
Study Day	-14 to -1	1	8	15	22	29	36	43	52	73	112	142	172	202	292	387
Clinical visit number	Screening	1	2	3	4	5	6		7	8	9			10	11	12
Days post 1 st dose			7	14	21											
Days post final dose						7	14	21	30	51	90	120	150	180	270	365
Windows (Days)		± 1							± 5		± 14				± 28	
General Assessments																
Informed consent	X															
Inclusion/ exclusion	X															
Demographics	X															
Medical history	X															
COVID-19 history of disease or exposure ^b	X	X	X	X	X	X	X	X	X	X	X	X	X	X	X	
Confirm contraceptive measures	X	X		C4 only	X				X							
Physical exam: height, weight ^c	X	X	X	C4 only	X	X			X		X			X	X	
Vital signs ^d	X	X	X	C4 only	X	X			X		X			X	X	
Concomitant medications	X	X	X	X	X	X	X	X	X	X	X	X	X	X	X	

Study Period	Baseline/ Screening ^a	Vaccine Administration and Initial Follow Up								Extended Follow Up						EOS
		1	8	15	22	29	36	43	52	73	112	142	172	202	292	
Study Day	-14 to -1															387
Clinical visit number	Screening	1	2	3	4	5	6		7	8	9			10	11	12
Days post 1 st dose			7	14	21											
Days post final dose						7	14	21	30	51	90	120	150	180	270	365
Subject training on AE diaries		X														
Issue diaries for solicited and unsolicited AEs		X		C4 only	X											
Review and collect solicited AE diary			X		C4 only	X										
Review and collect unsolicited AE diary			X	X	X	X	X	X	X							
In office AE collection ^e		X	X	X	X	X	X		X	X	X			X	X	X
Telephone safety follow up ^e								X				X	X			
Vaccine Administration																
Cohort 1		X ^f			X ^g											
Cohort 2		X ^f			X ^h											
Cohort 3		X ^h			X ^h											
Cohort 4		X ^f		X ^h	X ^h											
Cohort 5		X ^f			X ^h											

Study Period	Baseline/ Screening ^a	Vaccine Administration and Initial Follow Up							Extended Follow Up							EOS
		1	8	15	22	29	36	43	52	73	112	142	172	202	292	

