Study Day	-14 to -1															387
Clinical visit number	Screening	1	2	3	4	5	6		7	8	9			10	11	12
Days post 1 st dose			7	14	21											
Days post final dose						7	14	21	30	51	90	120	150	180	270	365
Laboratory Assessments																
Chemistry panel ^{a,i}	X	X	X	C4 only	X				X		X			X		
Hematology ^{a,j}	X	X	X	C4 only	X				X		X			X		
Urinalysis ^{a,k}	X	X	X	C4 only	X				X		X			X		
Collect biospecimens for SARS-CoV-2 testing ^a	X	X		C4 only	X				X		X			X	X	X
Collect whole blood/saliva for immunogenicity ^l		X		C4 only	X		X		X	X	X			X	X	X
Pregnancy test ^m	X	X		C4 only	X											

Abbreviations: C4, cohort 4

^a Day 1 chemistry, hematology, and urinalysis assessments do not need to be repeated if screening assessments were performed within 1 week prior to the start of treatment. Day 1 biospecimen collection for SARS-CoV-2 testing does not need to be repeated if screening assessments were performed within 72 hours prior to the start of treatment.

^b Potential exposure to SARS-CoV-2, symptoms of COVID-19, or outside testing results for SARS-CoV-2 infection will be collected at every study follow up visit and phone call.

- ^c Full physical examination will be performed at screening and symptom-directed (targeted) physical examination at all other time points if indicated. Height required at baseline/screening visit only.
- ^d Vital signs of temperature, heart rate, blood pressure, and respiratory rate will be assessed. Temperature will be documented upon collection of vital signs and subsequently if clinically indicated. Day 1 collection of vital signs does not need to be repeated if screening assessments were performed within 72 hours prior to the start of treatment.
- ^e Safety for the first 6 subjects enrolled will be assessed by telephone follow up 24 and 48 hours after receiving the priming vaccination. The ImmunityBio SRC will conduct a review of 48-hour safety data on the first 6 subjects; vaccination of additional subjects will proceed if no safety concerns are identified. In office AE collection will continue to occur for 1 year, but only applicable AEs will be collected (see [Section 7.2](#)).
- ^f Both hAd5-S-Fusion+N-ETSD (Suspension for injection) and hAd5-S-Fusion+N-ETSD (Oral capsule) will be administered. hAd5-S-Fusion+N-ETSD (Suspension for injection) will be administered either SC (subjects in cohorts 1, 2, and 4) or IM (subjects in cohort 5).
- ^g hAd5-S-Fusion+N-ETSD (Suspension for injection) will be administered SC only.

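### The early safety check covers the first six subjects enrolled, whatever their cohort, so it may include no intramuscular recipient

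*Combined protocol and SAP*

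**What the plan says.** All references are to the current synopsis and its schedules in the combined protocol and SAP, that is, the version with five evaluation cohorts.

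- **Study Design, stagger.** "Enrollment of the first 6 subjects will be staggered, with no more than 3 subjects enrolled per day for the first 2 days". Doses on those days are at least 3 hours apart. The six are telephoned at 24 and 48 hours after the prime, and the SRC reviews their 48-hour data. If that review raises no concern, dosing of further subjects goes ahead. No second hold point is described.
- **Table 10, footnote e.** It repeats the calls and the SRC review, but not the stagger: "Safety for the first 6 subjects enrolled will be assessed by telephone follow up 24 and 48 hours after receiving the priming vaccination".
- **Study Design, cohorts.** "subjects will be divided into 5 dosing cohorts with dosing schedule, mode of administration, and dosage as follows". There are 10 subjects per cohort, and the text gives no order or method of assignment.
- **Study Design, route.** "subjects in cohort 5 will be administered hAd5-S-Fusion+N-ETSD (Suspension for injection) via IM injection". Cohorts 1, 2 and 4 are injected SC, and cohort 3 receives capsules only.
- **Rationale and Purpose.** "Intramuscular (IM) administration of hAd5-based COVID-19 vaccines has not been explored in clinical trials, but hAd5 [E1-] vectors have been administered IM". The same section concludes that "hAd5-S-Fusion+N-ETSD (Suspension for injection) is well tolerated when administered to human subjects SC".
- **Study Design, solicited local events.** "Bleeding, bruising, and tingling/numbness will also be assessed following IM administration".
- **Table 10.** The row "In office AE collection ^e" is marked on day 1 and next on day 8, for all cohorts. Diaries are first reviewed on day 8, and the first telephone follow-up marked in the grid is day 43.

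**The concern.** The sponsor has decided that the first human exposures deserve a stagger, early calls and an SRC look before dosing continues. That safeguard is attached to order of enrolment, not to route. The one injection route with no trial experience for this class of vaccine can therefore start after the safeguard has been used up on SC or capsule-only subjects.

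Outside the first six, Table 10 shows no scheduled contact between day 1 and the day 8 visit. In-office collection on day 1 could catch an immediate injection-site event, but a reaction that develops over the next day or two would reach the site only through an unscheduled report or at day 8. What is at stake is exposure control: how many of the 10 cohort 5 subjects are injected IM before anyone has looked systematically at an IM recipient 48 hours after dosing. The texts do not contradict each other on this.

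**Working it through.** **The plan's own figures.** 3 per day × 2 days = 6 staggered subjects. 5 cohorts × 10 = 50 in the evaluation stage. 50 + 25 = 75 in total. All three agree with the synopsis.

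**Inputs.** 50 evaluation subjects, 10 of them IM (cohort table); a reviewed group of 6 (Study Design). Assignment order is not stated, so each row below is an assumption.

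**IM recipients among the first six**

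- *Balanced blocks of 5 (1 IM per block).* The first block contains exactly one IM subject, and the sixth subject is IM with probability 1/5. P(0) = 0, P(1) = 0.80, P(2) = 0.20.
- *Balanced blocks of 10 (2 IM per block).* P(0) = C(8,6)/C(10,6) = 28/210 = 0.133. P(1) = 2 × C(8,5)/210 = 112/210 = 0.533. P(2) = C(8,4)/210 = 70/210 = 0.333.
- *Random order over 50.* P(k) = C(10,k) × C(40,6−k)/C(50,6). P(0) = 0.2415, P(1) = 0.4141, P(2) = 0.2588. The expected number is 6 × 10/50 = 1.2.
- *Cohort 5 starts after the first six.* P(0) = 1. If cohorts fill in order 1 to 5, the first IM recipient is subject 41.
- *Cohort 5 fills first.* All six are IM, so P(0) = 0.

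| Assumed order | P(no IM in first 6) | P(fewer than 3 IM in first 6) |
|---|---|---|
| Blocks of 5 | 0% | 100% |
| Blocks of 10 | 13% | 100% |
| Random order | 24% | 91% (0.2415 + 0.4141 + 0.2588 = 0.914) |
| Cohort 5 after first six | 100% | 100% |
| Cohort 5 first | 0% | 0% |

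The threshold of 3 in the last column is the size of the sentinel group suggested below. It is not a figure from the plan.

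**What three sentinels would show.** The chance of at least one event is 1 − (1 − p)³ for true rate p:

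- p = 10%: 27%
- p = 20%: 49%
- p = 30%: 66%
- p = 50%: 88%

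**Exposure.** If no IM recipient is among the six, the visible plan allows all 10 to be dosed without an early SRC review of any of them. With three sentinels, the worst-case number dosed IM before a 48-hour review falls from 10 to 3.

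**The case against.** The strongest reply is that the copy available holds synopses and schedules only. The protocol body is absent and the Figure 1 schema is not shown, and either could give a cohort order or a hold for cohort 5. That limit is real and lowers confidence. It does not remove the point, because the release rule written in Study Design opens further dosing after the single review and has no route condition.

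Second, the added risk is modest. Cohort 5 differs from cohort 2 only in injection route. The suspension is described as tolerated SC in humans, and other hAd5 vectors and authorized vaccines have been given IM. Bleeding disorders that contraindicate injection are excluded, and the IM-specific local events are solicited by diary for 7 days. The capsule, for which the synopsis cites toxicity data only in rodents and primates, goes to every cohort on day 1, so any six subjects test it. All of this stands and is why the gap is called narrow. None of it is IM experience with this product.

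Third, the claim that all 10 might be dosed before any post-day-1 IM data are collected also needs cohort 5 to fill within about a week of its first dose, since day 8 visits (±1 day) would otherwise supply data. The documents give no enrolment rate. This condition must be stated. It does not affect the narrower statement that no 48-hour SRC review of an IM recipient is assured.

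Fourth, the probabilities span 0% to 100%, and the column for fewer than three uses a threshold the plan never set. That is fair: the figures show only that inclusion of an IM recipient is left to an unstated assignment scheme. Three sentinels would also miss a 10% event 73% of the time, so the gain lies in common reactions and limited exposure.

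**Conclusion.** The concern holds as a safety improvement worth considering, with medium confidence. As written, the stagger, early calls and SRC review do not guarantee that any IM recipient is seen. The chance of none among the six runs from 0% to 100% with the assumed assignment order, and is 24% in simple random order. In the worst case all 10 IM recipients are dosed with no 48-hour review. If cohort 5 also fills within about a week, they are dosed before any scheduled IM data after day 1 exist. The conclusion rests on the visible synopsis and Table 10, and a cohort-level hold in the protocol body or schema would answer it.

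**What to change.** In Study Design, add that the same stagger, 24- and 48-hour calls and SRC 48-hour review apply to the first IM recipients in cohort 5 before the rest of that cohort is dosed. Three is a reasonable number, counting any IM recipients already among the first six; the SRC should set it. Add the matching calls and review to Table 10 footnote e. If the protocol body already contains such a hold, state it in both places instead.

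The cost is one or two sentences in each place, plus any matching text in the body. With three sentinels and k IM recipients already among the six, the extra calls are 2 × max(0, 3 − k): 6, 4, 2 or 0 for k = 0, 1, 2 or at least 3. There would be at most one more review by the existing SRC. Cohort 5 would be delayed by a few days: 48 hours plus the SRC's review time, which the documents do not give.

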Safety: Safety endpoints include assessments of treatment-emergent MAAEs, SAEs, reactogenicity AEs, unsolicited AEs, safety laboratory tests, and vital signs. Toxicities will be graded using the Guidance for Industry: Toxicity Grading Scale for Healthy Adult and Adolescent Volunteers Enrolled in Preventive Vaccine Clinical Trials (2007).

Immunogenicity: Immunogenicity endpoints will include GMFR in IgG and additional antibody titers from baseline, and percentage of subjects who seroconverted defined as a 4-fold change in antibody titer from baseline. Neutralizing antibodies will be determined. ImmunityBio will calculate a relative IgG/Neutralization titer based on those data. CD8⁺ T-Cell activity against SARS-CoV-2 S protein and N protein will be measured by ELISPOT assay and CD4⁺ T-Cell activity against SARS-CoV-2 S protein and N protein will be measured by standard immune assays.

[figure not shown]
Statistical Methods:

The purpose of this study is to determine the safety, reactogenicity, and immunogenicity of the combination of hAd5-S-Fusion+N-ETSD (Suspension for injection) and hAd5-S-Fusion+N-ETSD (Oral capsule) and to select an optimal combination dose for future studies. Descriptive statistics will be presented for all study endpoints by individual cohort and for all cohorts combined.

Safety will be assessed by the incidence of treatment-emergent MAAEs, SAEs, and solicited local and systemic reactogenicity AEs, and unsolicited AEs for the time period of interest, overall and by grade using the Guidance for Industry: Toxicity Grading Scale for Healthy Adult and Adolescent Volunteers Enrolled in Preventive Vaccine Clinical Trials (2007). Clinically significant changes in safety laboratory tests and vital signs also will be summarized.

Immunology analyses will be used to provide an assessment of immune responses. Geometric mean fold rises (GMFRs) and geometric mean titers (GMTs) and their associated 95% confidence intervals (CIs) will be computed by exponentiation of the corresponding log-transformed means and 95% CIs. The percentage of subjects who seroconverted (as defined as 4-fold change in antibody titer relative to baseline) and 95% Clopper-Pearson CI will be summarized. Neutralizing antibody levels will also be summarized. CD8⁺ and CD4⁺ T-Cell activity also will be summarized.

Figure 1: Phase 1b Study Schema

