- ^h hAd5-S-Fusion+N-ETSD (Oral capsule) will be administered only.
- ⁱ See [Table 9](#) for additional details on laboratory assessments. Blood draws for lab assessments should occur prior to vaccine administration.
- ^j Hematology to include CBC with differential (5 part) as outlined in Table 9. Blood draws for lab assessments should occur prior to vaccine administration.
- ^k Urinalysis testing will include at a minimum protein, glucose, and presence of red blood cells. Sample collection should occur prior to vaccine administration.
- ^l Immunogenicity testing includes measures of antibody response and cell-mediated immunity against target antigens, as well as hAd5 serostatus for determining baseline hAd5 immunity and monitoring for antivector immune responses. Sample collection should occur prior to vaccine administration. A lab manual will be provided to the sites with detailed guidance for saliva collection, serum and PBMC preparation, storage, and shipping. Saliva and blood will be collected on all days indicated except days 10 (cohort 4 only) and 22, on which only blood will be collected.
- ^m Serum or urine pregnancy tests for females of childbearing potential at baseline/screening and at each visit where study drug is administered.

Table 11: Escalation Stage (Cohort 6): Schedule of Events

The schedule below shows assessments for each of the evaluation stage cohorts 1–5. Based on safety and immunogenicity data gathered from cohorts 1–5, one treatment regimen will be selected for administration to subjects in cohort 6; only the corresponding assessments will apply in this escalation stage.

Study Period	Baseline/ Screening ^a	Vaccine Administration and Initial Follow Up							Extended Follow Up						EOS	
		1	8	15	22	29	36	43	52	73	112	142	172	202	292	
Study Day	-14 to -1	1	8	15	22	29	36	43	52	73	112	142	172	202	292	387
Clinical visit number	Screening	1	2	3	4	5	6		7	8	9			10	11	12
Days post 1 st dose			7	14	21											
Days post final dose						7	14	21	30	51	90	120	150	180	270	365
Windows (Days)		± 1							± 5		± 14				± 28	
General Assessments																
Informed consent	X															
Inclusion/ exclusion	X															
Demographics	X															
Medical history	X															
COVID-19 history of disease or exposure ^b	X	X	X	X	X	X	X	X	X	X	X	X	X	X	X	X
Confirm contraceptive measures	X	X		C4 only	X				X							
Physical exam: height, weight ^c	X	X	X	C4 only	X	X			X		X			X	X	X

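### Cohorts 1 and 2 share one prime up to the day 22 pre-dose blood sample, but the synopsis plans no pooled day 22 summary of them; adding one would narrow the GMT or GMFR interval by about 35%.

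*Combined protocol and SAP*

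**What the plan says.** All references are to the latest synopsis in the file, the one with the IM cohort.

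- **Reporting.** Statistical Methods names two groupings: "Descriptive statistics will be presented for all study endpoints by individual cohort and for all cohorts combined". GMT and GMFR get 95% CIs formed on the log scale and exponentiated. Seroconversion gets a 95% Clopper-Pearson CI. T-cell activity is to be summarised, with no interval named.
- **Size.** "Up to 50 healthy subjects will be enrolled to evaluate the safety, reactogenicity, and immunogenicity of 5 different treatment regimens"; the Study Design table gives 10 per cohort. "Up to 25 additional subjects will be enrolled in the expansion stage of the study", and overall "Up to 75 subjects will be enrolled in this study".
- **Day 1.** The Study Design table gives cohorts 1 and 2 identical entries: SC 1×10^11 VP plus oral 1×10^10 IU. On route, "Subjects in cohorts 1, 2, and 4 will be administered hAd5-S-Fusion+N-ETSD (Suspension for injection) via SC injection".
- **Day 22.** Cohort 1 is boosted SC; cohorts 2, 3 and 5 are boosted orally. Cohort 4 has had an oral dose on day 15 as well.
- **Sampling.** Table 10 schedules immunogenicity samples on day 1, day 15 (cohort 4 only), day 22, day 36 and later. Its footnote on immunogenicity says: "Sample collection should occur prior to vaccine administration". On day 22 only blood is taken.
- **Purpose of the IM cohort.** The Rationale says IM was included so that its safety and immunogenicity could be compared with SC. One regimen is then chosen for cohort 6.

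**The concern.** Up to the day 22 draw, cohorts 1 and 2 have had exactly the same study treatment. If the cohorts are alike at entry, their day 22 antibody and T-cell results estimate one quantity, the response three weeks after a single SC plus oral prime. The design supplies 20 subjects for it.

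Neither named summary gives that estimate. The by-cohort columns split the 20 into two tens. At day 22 the all-cohorts column also holds an oral-only prime (cohort 3), an IM plus oral prime (cohort 5) and a cohort that has already had a second vaccination (cohort 4), so it describes no single prime.

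With 10 subjects per cohort, precision is scarce. At stake are the width of the post-prime SC plus oral estimate and of its comparison with the IM plus oral and oral-only primes. Timing matters too: in an open-label study, a pool named before the data are seen is more credible than one chosen afterwards.

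**Working it through.** **Plan's own figure.** 5 cohorts × 10 = 50, and 50 + 25 = 75, which agrees with the stated maximum. The documents give no power, SD or target precision, so there is nothing further to reproduce.

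**Who can be pooled at day 22 (pre-dose)**

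| Cohort | Vaccination before the day 22 sample | Same as cohort 1? |
|---|---|---|
| 1 | SC + oral, day 1 | – |
| 2 | SC + oral, day 1 | Yes |
| 3 | Oral, day 1 | No |
| 4 | SC + oral, day 1; oral, day 15 | No |
| 5 | IM + oral, day 1 | No |

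For cohorts 1 and 2, day 22 is the only scheduled immunogenicity sample between prime and boost.

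**GMT or GMFR, one group.** The half-width of the 95% CI on the log scale is t(0.975, n−1) × SD / √n.

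- n = 10: 2.262 / √10 = 0.715 SD
- n = 20: 2.093 / √20 = 0.468 SD
- Ratio 0.468 / 0.715 = 0.654, so the interval is 34.6% narrower. The SD cancels.
- Standard error alone: 1 − √(10/20) = 29.3% smaller.

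The result is stable. With 8 or 9 evaluable per cohort the narrowing is 36.3% or 35.3%; with a within-cohort SD on 18 df it is 34.3%. If the true cohort means differ by d SD, the pooled half-width is multiplied by √(1 + d²/4), and the narrowing is about 33% at d = 0.5 and 27% at d = 1.

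**On the fold scale (assumed SDs; the documents give none).** The CI multiplies and divides the GMT by 10^(half-width × SD).

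| Assumed log10 SD | n = 10 | n = 20 |
|---|---|---|
| 0.3 | 1.64 | 1.38 |
| 0.5 | 2.28 | 1.71 |

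**Seroconversion, Clopper-Pearson.** 5/10 gives 18.7–81.3% (62.6 points); 10/20 gives 27.2–72.8% (45.6 points). 1 − 45.6/62.6 = 27% narrower. Narrowing is 29% at 80%, 31% at 90% and 45% at 100%.

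**IM plus oral (cohort 5) v SC plus oral.** The synopsis names no between-cohort interval; this is what a reader would obtain, assuming a common SD. The half-width is t × SD × √(1/n1 + 1/n2).

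- 10 v 10: t(18) × √0.20 = 0.940 SD
- 10 v 20: t(28) × √0.15 = 0.793 SD
- Ratio 0.844, so about 16% narrower. At an assumed SD of 0.5 log10, the factor goes from 2.95 to 2.49.

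**Cohort 1 v cohort 2 as a check.** This is also 10 v 10, with half-width 0.94 SD. An observed gap smaller than that leaves zero inside the interval.

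**The case against.** The strongest case against is that this is a descriptive study whose aim is to choose a regimen. Cohorts 1 and 2 are different regimens, so by-cohort reporting fits that aim, and pooling them cannot help choose between them. The samples are drawn and assayed in any case, and the pooled row can be produced at any time. All of this stands, and it limits the point to one extra summary at one visit.

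Two further objections stand in part. First, the text says only that subjects are divided among cohorts; no randomisation is described, so it is an assumption that cohorts 1 and 2 are alike. A narrower interval also does nothing about bias in the comparison with cohort 5. Secondly, the source is a synopsis that points to sections not supplied. It says what will be presented and does not rule out other summaries; if the full statistical section already names this pool, no change is needed.

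A reader might infer three stronger things that the documents do not support.

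- *That day 22 is the only point at which IM can be compared with SC, or injection plus capsule with capsule alone.* Cohorts 2, 3 and 5 receive the same oral boost on day 22, so 5 v 2 and 2 v 3 remain like-for-like at every later visit. Day 22 is distinctive only because cohort 1 can be added to cohort 2 there.
- *That a third of the precision is lost throughout.* The 35% applies to the width of a one-group GMT or GMFR interval at day 22. The IM v SC interval gains 16%, and results after the boost gain nothing.
- *That agreement between cohorts 1 and 2 would validate the pool.* With a half-width of 0.94 SD, a moderate imbalance could easily go unseen.

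**Conclusion.** The point holds as a minor, inexpensive improvement in planned reporting. It is not an error that threatens a conclusion. On the synopsis as supplied, the 20-subject post-prime estimate is not among the named summaries, and adding it gives the gains shown in the working. The percentage gains for GMT, GMFR and the IM v SC interval do not depend on the SD; every fold figure does, and rests on an assumed log10 SD of 0.3 to 0.5.

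The conclusion assumes 10 evaluable subjects per cohort (the planned maximum), day 22 blood actually drawn before dosing, and cohorts 1 and 2 comparable at entry. The last assumption is the weakest, so the pooled figure should supplement the by-cohort figures and not replace them.

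**What to change.** Keep the by-cohort summaries and add to Statistical Methods wording such as:

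> For the day 22 pre-dose blood sample, cohorts 1 and 2 will also be pooled (SC plus oral prime, planned n = 20) for GMT, GMFR, seroconversion and T-cell activity, and shown beside cohort 3 (oral prime) and cohort 5 (IM plus oral prime). The cohort 1 v cohort 2 difference at this sample will be reported with its 95% CI, descriptively.

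Cohort 4 stays out because of its day 15 dose.

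The cost is one table column and one line for the difference, with no new subjects, samples or assays and no effect on dosing. The downside is the comparability assumption. A table note should say that no randomisation between the cohorts is described, and that a small observed difference on 10 v 10 does not establish comparability.
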